6.2.8 Missing Diagnosis Dates

If the month and year are present but the day is missing, the diagnosis date will be set to first day of the relevant month. If only the year is recorded the diagnosis date will be set as "01-Jan" for that year.

6.2.9 Exposure to Study Drug

Exposure to study drug will be calculated from the date of last dosing minus the first day of dosing (in AURORA 2) + 1 for each prescribing record. Exposure will be summarized as the number of days on medication and mean daily dose. Mean daily dose will take into account periods where zero dose was prescribed.

6.2.10 Inexact Values

In the case where a variable is recorded as "> x", "≥ x", "< x" or "≤ x", a value of x will be taken for analysis purposes.

6.2.11 Electrocardiogram (ECG) Data

For ECG data recorded on continuous scales, if more than one value is recorded at a time point, the mean value rounded to the integer will be presented. For overall interpretation if more than one value is recorded, the most severe (worst case) of the respective readings will be taken.

6.2.12 Unscheduled Visits

All visits whether scheduled or unscheduled will be mapped to the closest scheduled protocol visit according to the protocol schedule of assessments. However, visits, when sorted by visit number and visit date, must remain in chronological order. In summary tables by visit, a subject's latest observation per visit will be tabulated.

QMD Ref: [REDACTED]	Effective: 12Aug2019	Governing QMD: [REDACTED]
Confidentiality Statement		
This document is the property of [REDACTED] and may not be duplicated, copied, altered or removed from company without prior approval from [REDACTED] or in compliance with [REDACTED].		

REF: [REDACTED]

		Controlled Quality Management Document	
		Sponsor:	Aurinia Pharmaceuticals
		Protocol Number:	AUR-VCS-2016-02
STATISTICAL ANALYSIS PLAN. PHASE 2-3-4			

6.2.13 Randomization Strata

The randomization will be stratified by biopsy class (Class V only versus Others) and by prior mycophenolate mofetil (MMF) use at time of screening. A regional blocking factor will also be used for supply purposes ensuring balance within region. The stratification factors and the regional blocking factor will be used as covariates in the primary analyses.

Variables for biopsy class data and prior MMF use will be taken from AURORA 1 data.

6.2.14 eGFR

For the purposes of all eGFR summary tables and endpoints incorporating eGFR measures, an eGFR ceiling will be set at 90 mL/min/1.73 m². In doing so, all values greater than 90 will be constrained to 90, thereby removing the reductions from renal hyperfiltration to normal renal function. These eGFR values will be labelled as ‘Corrected eGFR’. Original, raw- eGFR measures will be displayed in listings. In addition, eGFR change from baseline tables will be produced using raw-eGFR values.

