6.3 Conventions

All data listings, summaries, figures and statistical analyses will be generated using SAS version 9.4 or higher¹.

Summaries will be presented by treatment group for all subjects. Treatment group labels will be displayed as follows:

- Placebo
- Voclosporin
- Overall

Columns to be included within the table shells are as follows:

Demography	Treatment group and overall
Baseline	Treatment group and overall
Disposition	Treatment group and overall
Efficacy	Treatment group
TEAEs	Treatment group
Other safety	Treatment group

Tables of events or medications will be ordered in descending frequency of subjects followed by (where applicable) events for the system organ class (or Anatomical Therapeutic Chemical Classification System [ATC] level 2 for medications) followed by the preferred term. Ordering will be for the voclosporin treatment group first followed by the placebo group and alphabetical thereafter.

Listings will be sorted in the following order: treatment group, subject, parameter, and visit unless otherwise stated. All data will be listed.

Continuous variables will be summarized by the number of non-missing observations, mean, median, standard deviation, and minimum and maximum. For all tabulations of changes from baseline data, the lower and upper 95% confidence limits for the mean for the individual treatments will be given.

QMD Ref: [REDACTED]	Effective: 12Aug2019	Governing QMD: [REDACTED]
Confidentiality Statement		
This document is the property of [REDACTED] and may not be duplicated, copied, altered or removed from company without prior approval from [REDACTED] or in compliance with [REDACTED].		

		Controlled Quality Management Document	
		Sponsor:	Aurinia Pharmaceuticals
		Protocol Number:	AUR-VCS-2016-02
STATISTICAL ANALYSIS PLAN. PHASE 2-3-4			

Categorical variables will be summarized by presenting the frequency and percent. Percentages will be based on the number of non-missing observations out of the subject population unless otherwise specified. For each variable, all categories will be shown. Zero frequencies (but not the percent) within a category will be presented.

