6.11.2.4 Change from Baseline Endpoints

The following endpoints are included in change from baseline endpoints:

- Change in SELENA-SLEDAI scores from AURORA 1 baseline at Months 6, 12, 18, 24 and 36. Change from baseline in SELENA-SLEDAI total score will be the response

QMD Ref: [REDACTED]	Effective: 12Aug2019	Governing QMD: [REDACTED]
Confidentiality Statement		
This document is the property of [REDACTED] and may not be duplicated, copied, altered or removed from company without prior approval from [REDACTED] or in compliance with [REDACTED].		
REF: [REDACTED]		Page 25 of 37

		Controlled Quality Management Document	
		Sponsor:	Aurinia Pharmaceuticals
		Protocol Number:	AUR-VCS-2016-02
STATISTICAL ANALYSIS PLAN. PHASE 2-3-4			

variable in the Mixed Effect Model Repeated Measures (MMRM) model. The scores of the individual SELENA-SLEDAI items and the total score of each subject will be listed.

- Change in UPCR, eGFR, urine protein, and serum creatinine from AURORA 1 baseline at Months 6, 12, 15, 18, 21, 24, 27, 30, 33 and 36.
- Changes in eGFR between last on-treatment value and last off-treatment values will also be summarized.
- Change in immunology parameters (C3, C4, and anti-dsDNA) from AURORA 1 baseline at Months 6, 12, 15, 18, 21, 24, 27, 30, 33 and 36.
- Change in HRQoL (SF-36) from AURORA 1 baseline at Months 6, 12, 18, 24, 30, and 36. Only the scales (Physical functioning, Role limitations due to physical health, Role limitations due to emotional problems, Energy/fatigue, Emotional well-being, Social functioning, Pain, General health, Total Mean Score) will be summarized. MMRM will be performed only for Total Mean Score. The individual items and scales will be listed.

Change from baseline endpoints will be summarized using descriptive statistics for observed values and changes from baseline by treatment group. All data will be listed.

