Change from baseline will be analyzed using a MMRM analysis with treatment arm, visit, treatment by visit interaction, biopsy class, MMF use at baseline, region and baseline value included as a covariates in the model. Results will be expressed as differences between treatment arms (along with the associated 95% CI). The observed and change from baseline values will be summarized by treatment visit and treatment arms. The Least Squares (LS) means and their corresponding 95% CI of the change from baseline values will also be presented for each visit and for the overall change. The model will be fitted using an unstructured (UN) covariance matrix. Should the UN covariance matrix not converge, then an autoregressive (AR(1)) covariance matrix will be used. The covariance matrix used will be indicated in the footnotes. The Kenward-Roger degree of freedom adjustment will be applied. LS mean plots of mean change from baseline versus visit will be presented for UPCR and eGFR.

QMD Ref: [REDACTED]	Effective: 12Aug2019	Governing QMD: [REDACTED]
Confidentiality Statement		
This document is the property of [REDACTED] and may not be duplicated, copied, altered or removed from company without prior approval from [REDACTED] or in compliance with [REDACTED].		

REF: [REDACTED]

		Controlled Quality Management Document	
		Sponsor:	Aurinia Pharmaceuticals
		Protocol Number:	AUR-VCS-2016-02
STATISTICAL ANALYSIS PLAN. PHASE 2-3-4			

The SAS code anticipated to be used for analysis of the change from baseline endpoints is as follows:

```
proc mixed data=dataset;
class subject treatment visit biopsy class mmf use region;
model response = treatment visit treatment*visit biopsy_class mmf_use region
baseline / ddfm=kr
repeated visit / subject=subject type=un r corr;
lsmeans visit*treatment / pdiff cl e;
run;
```

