Blood Chemistry	Alanine aminotransferase (ALT)	All visits
	Albumin	All visits
	Alkaline phosphatase (ALP)	All visits
	Aspartate aminotransferase (AST)	All visits
	Bicarbonate	All visits
	Bilirubin (direct and total)	All visits
	Blood urea nitrogen (BUN)	All visits
	Calcium	All visits
	Chloride	All visits
	Cholesterol (total, HDL, and LDL)	Month 24 and Month 36
	Creatine kinase	Every 6 months
	Creatinine	All visits
	Gamma-glutamyl transferase (GGT)	All visits
	Glucose	All visits
	Glycosolated hemoglobin (HbA1c)	Annually
	Lactic dehydrogenase (LDH)	All visits
	Magnesium	All visits
	Phosphorous, inorganic	All visits
	Potassium	All visits
	Protein, total	All visits
Sodium	All visits	
Triglycerides	Annually	
C-reactive Protein	All visits	

Test Type	Test Parameters	Collection at Visits
Urinalysis	Complete urinalysis (to include urine protein, creatinine, blood, urine microscopy).	All visits

QMD Ref: [REDACTED]	Effective: 12Aug2019	Governing QMD: [REDACTED]
Confidentiality Statement		
This document is the property of [REDACTED] and may not be duplicated, copied, altered or removed from company without prior approval from [REDACTED] or in compliance with [REDACTED].		

REF: [REDACTED]

		Controlled Quality Management Document	
		Sponsor:	Aurinia Pharmaceuticals
		Protocol Number:	AUR-VCS-2016-02
STATISTICAL ANALYSIS PLAN. PHASE 2-3-4			

Test Type	Test Parameters	Collection at Visits
Proteinuria	FMV will be performed to analyze UPCR. A 24-hour urine may be substituted for FMV if required.	All visits
	FMV	All visits
	24-hour urine	Every 6 months

Test Type	Test Parameters	Collection at Visits
Pregnancy Test	A serum pregnancy test will be performed for females of childbearing potential. Urine pregnancy tests will be done using a dipstick.	Month 12, Month 24, and Month 36 (Serum)
		Month 12, Month 15, Month 18, Month 21, Month 27, Month 30, Month 33 (Urine)

Test Type	Test Parameters	Collection at Visits
Lupus Markers	Anti-double-stranded DNA (anti-dsDNA) antibodies	All visits
	Serum	All visits
	Complement 3 Complement 4	
Special Tests	Estimated glomerular filtration rate (eGFR)	All visits

Additional eGFR tables will summarize changes from last on treatment value to last off treatment value. The slope of eGFR over time will also be summarized. eGFR slope will be assessed from AURORA 1 baseline to Week 4 and then from Week 4 through to the end of AURORA 2.

A listing of all laboratory measurements recorded throughout the study will be presented.

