7 INTERIM ANALYSIS

The study will be ongoing during regulatory interaction and as such, regular reporting events will be required to ensure authorities are provided the most up to date information available.

These reporting events will incorporate both safety and efficacy analyses.

Timing of the interim analyses will range from 3 months post the final subject final visit of the AURORA 1 study (i.e., when the last subject reaches Month 15 of the AURORA 2 continuation study) up to 6 months prior to the end of AURORA 2 (i.e., when the last subject reaches Month 30 of the AURORA 2 continuation study).

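### The ceiling of 90 applies to both eGFR slopes and the last-on/last-off tables with no raw version specified, and the later slope mixes on- and off-drug values to an undefined last visit

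*SAP*

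**What the plan says.** SAP 6.2.14 (eGFR) sets the rule: "For the purposes of all eGFR summary tables and endpoints incorporating eGFR measures, an eGFR ceiling will be set at 90" mL/min/1.73 m². Its stated aim is "thereby removing the reductions from renal hyperfiltration to normal renal function". Raw values go into listings, with one further exception: "In addition, eGFR change from baseline tables will be produced using raw-eGFR values".

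The SAP then plans these eGFR outputs:

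- **Slopes (SAP 6.12.2):** "eGFR slope will be assessed from AURORA 1 baseline to Week 4 and then from Week 4 through to the end of AURORA 2". Nothing is said about raw values or about on-treatment values.
- **Last-on/last-off (SAP 6.11.2.4, and again in 6.12.2 as additional tables):** "Changes in eGFR between last on-treatment value and last off-treatment values will also be summarized". No raw or corrected label is given.
- **MMRM of change from AURORA 1 baseline (SAP 6.11.2.4):** between-arm differences with 95% CIs, and "LS mean plots of mean change from baseline versus visit will be presented for UPCR and eGFR". No raw or corrected label is given.
- **Change tables in general (SAP 6.3):** "the lower and upper 95% confidence limits for the mean for the individual treatments will be given".

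The end of the later slope is not given as a visit. SAP 7 describes an interim analysis "up to 6 months prior to the end of AURORA 2 (i.e., when the last subject reaches Month 30", which puts the end of AURORA 2 at Month 36. Protocol 4.1 also has eGFR measured at the Month 37 follow-up visit, after the last dose. Protocol 5.6 keeps subjects who stop study treatment in scheduled visits up to Month 36 where possible. SAP 6.11.4 lists sensitivity analysis as not applicable.

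**The concern.** Long-term safety is the primary objective, and the slopes are the SAP's direct summary of how fast eGFR is lost. Two features can make that loss look smaller than it is.

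First, a fall that stays above 90 counts as zero once capped, and a fall that crosses 90 counts only in part. Protocol 7.6.1.5 asks investigators to monitor falls of more than 30% that stay above 90, so the protocol does not treat such falls as empty of information.

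Second, Protocol 2.1 calls the renal-function risk reversible. If eGFR recovers after drug is stopped, the recovery enters the later slope as slower loss, and no on-treatment slope is planned beside it.

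A reader of the study report could then see flat slopes without being able to tell whether they reflect stable function, the ceiling, or off-drug recovery.

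**Working it through.** The documents give no slope, baseline eGFR distribution or expected eGFR effect, so there is no planned figure to reproduce. The one relevant number is in Protocol 1.2.4.2: a median fall of 8–9 mL/min by Week 4 in the Phase 2 voclosporin groups, then stabilization. It is a within-group figure with no placebo change beside it. All other inputs below are assumptions, shown as ranges.

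**1. Which outputs have a raw version.** The general rule in SAP 6.2.14 is capped; the exceptions are listings and change-from-baseline tables. A slope is not a change-from-baseline table. Last-on/last-off takes the last on-treatment value as its reference, so it is not a change from baseline either, although SAP 6.11.2.4 lists it under that heading. The MMRM does model change from baseline and could be covered by the exception.

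**2. Single subjects** (baseline, Week 4, Month 36; later slope = difference ÷ 35/12 years).

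| Raw values | Raw early change; later slope | Capped early change; later slope |
|---|---|---|
| 120, 111, 91 | −9; −6.9/year | 0; 0 |
| 110, 101, 85 | −9; −5.5/year | 0; −1.7/year |
| 85, 76.5, 60 | −8.5; −5.7/year | −8.5; −5.7/year |

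**3. Between-arm difference under the cap.** Take X ~ N(μ, σ) and z = (90 − μ)/σ. Then E[min(X, 90)] = μΦ(z) − σφ(z) + 90(1 − Φ(z)). The capped difference for a true difference d is this value at μ minus the value at μ − d. Example: μ = 90, σ = 25, d = 8.5 gives 80.03 − 75.21 = 4.82.

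| True d | μ = 80 | μ = 90 | μ = 100 |
|---|---|---|---|
| 3 | 2.0 | 1.6 | 1.1–1.2 |
| 5 | 3.3–3.5 | 2.7 | 1.9–2.0 |
| 8.5 | 5.8–6.1 | 4.7–4.8 | 3.5–3.6 |
| Share kept | 65–72% | 52–57% | 37–42% |

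Ranges are over σ = 25 and 30.

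**4. Later slope under the cap.** I applied the same expectation at each visit and fitted a least-squares slope over Months 1, 3, 6, 9, 12 and then every 3 months to 36 (the visits before Month 12 are assumed). For a true loss of 2–4 mL/min/year starting from mean 80, 90 or 100, the share kept is 67–74%, 54–60% and 39–45%. If an 8.5 mL/min early fall comes first, fewer subjects sit above 90 and the shares rise to 76–84%, 65–72% and 52–57%. With zero true loss the cap has nothing to shrink.

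**5. Renal response.** The cap can alter the eGFR criterion only when baseline exceeds 90 and the value is below 60. The fall is then more than 33% on either scale, because (90 − 60)/90 = 33%, so the 20% threshold is passed both ways. A grid of integer baselines 20–160 and values 5–160 (141 × 156 = 21,996 pairs) gives 0 disagreements.

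**6. Off-drug values.** A rebound of size r after stopping at month m changes a subject's raw slope by r × Σ(t − t̄, visits after m) ÷ Σ(t − t̄)², with t̄ = 1.506 years and Σ(t − t̄)² = 11.13 on the schedule above. For r = 8.5 (full reversal, assumed) this is 3.98, 3.42 and 2.09 mL/min/year for stopping at Months 18, 24 and 30. The planned slope is capped, however, and the cap shrinks the rebound too. With baseline mean 80–100, SD 25–30, within-subject SD 8–10, an 8.5 early fall and later loss of 0–4/year, the effect is 1.65–3.27, 1.41–2.82 and 0.86–1.74, so about 0.9–3.3 overall. At arm level this is multiplied by the fraction who stop.

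**The case against.** The cap has a stated reason, and Protocol 7.6.1 says eGFR may be unreliable above 100. That stands: the point is a missing companion analysis, and the capped analyses should stay.

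The raw exception may be meant to cover the whole of SAP 6.11.2.4, including the MMRM and its between-arm differences. That is a plausible reading for the MMRM, so a reader should not infer that no raw between-arm eGFR comparison is planned. Only a label is missing there. The reading does not reach the slopes.

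Other checks exist: an MMRM of serum creatinine, which the ceiling does not touch, raw change tables and raw listings. They help, but none gives a raw slope.

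The slope is a descriptive summary, not a listed endpoint, and the direction of the off-drug effect is not established. Protocol 5.6.1 takes subjects who need rescue off study treatment as treatment failures; their eGFR could fall afterwards and steepen the slope. This stands, so rebound is an assumption and not a finding.

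An on-treatment slope has its own selection problem, because it loses later values from subjects whose drug is withheld for eGFR falls (Protocol 7.6.1.1). This also stands, and is why both slopes should be shown.

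Finally, part of the SAP next to the slope text was not available. Statements that something is not specified cover only the text that was.

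**Conclusion.** The gap is real and limited. By the SAP's own rule, both slopes and the last-on/last-off tables are capped with no raw version in the available text. The MMRM is unlabelled. The later slope combines on- and off-drug values, and its last visit is inferred, not stated.

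If there is true loss, the cap shrinks it materially whenever many subjects sit above 90: about 37–72% of a between-arm difference and 39–74% of a later loss remain, on the assumed distributions. These figures are illustrations, because the documents do not report the share of subjects above 90.

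Four stronger readings are not supported:

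- Raw eGFR is not absent from the plan; listings and change tables use it.
- The cap does not inflate renal response.
- The uncapped rebound effect of 2.1–4.0 mL/min/year does not describe the planned slope; 0.9–3.3 does, for one subject who stops and fully rebounds.
- The plan is not shown to favour voclosporin. The cap shrinks placebo falls too, and the Phase 2 account of stabilization after Week 4 would leave the cap little to shrink in the later slope.

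The change should be made because it is cheap and bears on the primary objective.

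**What to change.** Keep every capped analysis and add the following to the SAP:

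1. Label each eGFR output raw or corrected, and say whether the raw change-from-baseline tables in 6.2.14 include the MMRM and the LS mean plots.
2. Add raw versions of both slopes, the last-on/last-off tables and, if not already meant, the MMRM.
3. Name the last visit in the later slope and exclude the off-drug Month 37 value.
4. Show an on-treatment later slope beside the all-visits slope, with a stated rule for values during and after interruptions.

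The cost is SAP wording and a few tables, with no new data. Raw values at high eGFR are noisier and the on-treatment slope loses values selectively, so neither addition should replace what is already planned.

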6.2.15 FMV and 24-hour Urine

UPCR values will be determined using first morning void (FMV) urinalysis samples. In the event that the Investigator determines that the Month 12, Month 18, Month 24, Month 30 or Month 36 FMV urinalysis sample was invalid, the UPCR values from the 24-hour urinalysis at the corresponding visit will be used instead of the FMV urinalysis in the calculation of efficacy endpoints. FMV analysis results will still be used for all other timepoints.

6.2.16 Adverse Events

An AE with missing intensity of AE will be coded “Severe” which is the worst case. An AE with a missing relationship to Study Drug will be coded as “Related”. An AE with missing relationship to disease under Study will be coded as “Related” to the disease unless the AE is recorded as being related to treatment.

6.2.17 SELENA-SLEDAI Index Score

The SELENA-SLEDAI assesses disease activity within the last 10 days. Twenty-four items are scored for 9 organ systems and summed to a maximum of 105 points. A score of 6 is considered clinically significant. Assessments for SELENA-SLEDAI will be conducted at AURORA 1 baseline and Week 52, and Months 18, 24 and 36.

QMD Ref: [REDACTED]	Effective: 12Aug2019	Governing QMD: [REDACTED]
Confidentiality Statement		
This document is the property of [REDACTED] and may not be duplicated, copied, altered or removed from company without prior approval from [REDACTED] or in compliance with [REDACTED].		

		Controlled Quality Management Document	
		Sponsor:	Aurinia Pharmaceuticals
		Protocol Number:	AUR-VCS-2016-02
STATISTICAL ANALYSIS PLAN. PHASE 2-3-4			

While the total score is populated on the database, it will be re-calculated as the sum of all individual items and added to the efficacy ADaM. Any missing items will lead to a missing total.

A patient's SELENA-SLEDAI total score at a given visit is the sum of the weighted scores of all marked SLE-related descriptors. A total score can fall between 0 and 105, with a higher score representing a more significant degree of disease activity.

6.2.18 Short Form Health Survey (SF-36)

The SF-36 HRQoL assessment is a 36-question subject HRQoL questionnaire. The SF-36 responses will be weighted as follows:

Item number	Original Response	Weight
1, 2, 20, 22, 34, 36	1 →	100
	2 →	75
	3 →	50
	4 →	25
	5 →	0
3, 4, 5, 6, 7, 8, 9, 10, 11, 12	1 →	0
	2 →	50
	3 →	100
13, 14, 15, 16, 17, 18, 19	1 →	0
	2 →	100
21, 23, 26, 27, 30	1 →	100
	2 →	80
	3 →	60
	4 →	40
	5 →	20
	6 →	0

QMD Ref: [REDACTED]	Effective: 12Aug2019	Governing QMD: [REDACTED]
Confidentiality Statement		
This document is the property of [REDACTED] and may not be duplicated, copied, altered or removed from company without prior approval from [REDACTED] or in compliance with [REDACTED].		

REF: [REDACTED]

		Controlled Quality Management Document	
		Sponsor:	Aurinia Pharmaceuticals
		Protocol Number:	AUR-VCS-2016-02
STATISTICAL ANALYSIS PLAN. PHASE 2-3-4			

Item number	Original Response	Weight
24, 25, 28, 29, 31	1 →	0
	2 →	20
	3 →	40
	4 →	60
	5 →	80
	6 →	100
32, 33, 35	1 →	0
	2 →	25
	3 →	50
	4 →	75
	5 →	100

These items will be further grouped into the following scales:

Scales	Number of items	Mean of Items
Physical functioning	10	3, 4, 5, 6, 7, 8, 9, 10, 11, 12
Role limitations due to physical health	4	13, 14, 15, 16
Role limitations due to emotional problems	3	17, 18, 19
Energy/fatigue	4	23, 27, 29, 31
Emotional well-being	5	24, 25, 26, 28, 30
Social functioning	2	20, 32
Pain	2	21, 22
General health	5	1, 33, 34, 35, 36
Total mean score	36	All 36 items

QMD Ref: [REDACTED]	Effective: 12Aug2019	Governing QMD: [REDACTED]
Confidentiality Statement		
This document is the property of [REDACTED] and may not be duplicated, copied, altered or removed from company without prior approval from [REDACTED] or in compliance with [REDACTED].		

REF: [REDACTED]

		Controlled Quality Management Document	
		Sponsor:	Aurinia Pharmaceuticals
		Protocol Number:	AUR-VCS-2016-02
STATISTICAL ANALYSIS PLAN. PHASE 2-3-4			

Each scale will be calculated for each subject by taking the mean of its corresponding item.

Only scheduled post-baseline laboratory and vital signs values will be tabulated. Post-baseline repeat / unscheduled assessments will be disregarded, although these post-baseline assessments will be listed in the relevant appendices to the CSR.

